## **9 STATISTICAL & DATA ANALYSIS**

### **STATISTICAL ANALYSIS**

Sandri et al. (2005, Study A, patients with peripheral arterial occlusive disease) found that in the control group, CD34+ cells increased from 372 cells per mL blood at baseline (SD 156) to 402 (SD 183) at 4 weeks. In their exercise training group, the increase was from 458 (SD 252) at baseline to 2977 (SD 852) at 4-weeks. We created a simulated data set with these parameters in order to calculate the percent of CD34+ cell variation that was explained by the group x time interaction. We tested two random effects mixed models, one without and the other with, a group x time interaction (group is treatment vs control; time is pre vs. 4-weeks post). The percent variance explained =  $(V_{no-int} - V_{int})/V_{no-int}$ , where  $V_{no-int}$  is the residual covariance parameter estimate without a group x time interaction term in the model, and  $V_{int}$  is the residual covariance parameter estimate with a group x time interaction term in the model. We found that based on the baseline and 4-week mean and standard deviation of CD34+ cell concentrations reported by Sandri et al., the interaction explained 84.5% of the variance in CD34+ cell concentration (a very large effect size). The correlation among repeated measures was  $r=.62$ . Using these parameters in G-Power3 (version 3.1.3), with 2 groups measured at 2 time points, in order to achieve power  $>.95$  would require a total sample size of 6 subjects (3 per group) each measured at 2 time points. If the group x time interaction explained only 50% of the variance in CD34+ cell count (still a large effect), we would need sample size of 8 (4 per group) in order to achieve power  $>.95$ , if only two groups are present.

In another study, Sen et al., in a sample of patients with pre-diabetes (n=11), CD34+ cell number increased from 0.8 (SEM 0.1) before exercise, to 1.4 (SEM 0.2) after exercise, a pre-post effect size (Cohen's d) of 1.81.

Taking multiple study observation factors, in order to detect an effect of this size using a 2-tailed paired t-test, with alpha=.05, for power  $>.95$ , the number of subjects required would be 7-8, per group.

However, these two quoted studies are different from our proposed study on patients with diabetes. It is well known that diabetes can affect CD34+ number and function, therefore in our proposed study the number of CD34+ cells available from the subjects may be a limiting factor. *Therefore, we propose to enroll 45 and retain 36 patients (10 subjects per group), in order to safely determine the effect of two individual groups of Dapa alone and Dapa+Saxagliptin combination with adequate number of CD34+ cells available for all proposed cellular outcome measures.*

Power calculation based on Sandri et al emphasizes CD34+ cell number and our recent study which looked at one of the medications being tested in this current combination protocol [41] takes into consideration CD34+ cell function and gene expression which verified our current statistical calculation. Our study actually demonstrated the validity of CD34 function and gene expression measures which were statistically significant.

However, this current study protocol describes a different cohort than Dore/Domingues et al [41] and similar to cohort described in Sandri et al (that is subjects with CVD). Currently there is no published study on progenitor cells looking at SGLT-2 inhibitor or in combination with a DPP4 inhibitor that we can base our calculations on and the closest will be our published study. [41].

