### **DATA ANALYSIS**

We will use generalized estimating equations (GEE) with robust standard error estimates to model within-subject and between-group differences over time. First we will investigate whether an unstructured correlation matrix is best fitting for the error term based on examination of the working correlation matrix output. If an exchangeable structure fits the data, we will consider using a random-effects mixed model with restricted maximum likelihood, due to its weaker assumption for missing data on the response variable. Using either approach, of primary interest will be the group (drug treatment) by time interaction, which will tell us whether the change in the dependent variable over time differs between groups. We will include as covariates any pre-treatment variables (e.g., demographics, baseline levels of the dependent variable, comorbidities, laboratory test values) that differ between groups even at a trend level of significance ( $p < .10$ ).

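### The printed pre-diabetes figures do not establish 7-8 subjects per group, and a within-arm paired test does not size the group-by-time interaction

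*Combined protocol and SAP*

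**What the plan says.** Section 9, Statistical Analysis, gives two pieces of support for the sample size.

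- **Exercise study in peripheral arterial disease.** A simulated two-group, two-time-point data set is used to express the group-by-time interaction as a share of residual variance: 84.5%, with a repeated-measures correlation of .62. This leads to 6 subjects in total. For a 50% share the plan says "we would need sample size of 8 (4 per group) in order to achieve power" above .95, with the condition "if only two groups are present".
- **Exercise study in pre-diabetes (n=11).** The plan reports that "CD34+ cell number increased from 0.8 (SEM 0.1) before exercise, to 1.4 (SEM 0.2) after exercise, a pre-post effect size" of 1.81 (Cohen's d). For an effect of that size, "using a 2-tailed paired t-test, with alpha=.05" and power above .95, it says "the number of subjects required would be 7-8, per group". It prints neither the denominator of d nor a pre-post correlation for this study.

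The plan then says that "these two quoted studies are different from our proposed study on patients with diabetes", and continues: "we propose to enroll 45 and retain 36 patients (10 subjects per group". The Synopsis and section 4 (Study Design and Duration) give 12 retained per arm. Section 8 (Study Design Overview) gives 10.

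Section 9, Data Analysis, says that "of primary interest will be the group (drug treatment) by time interaction". The trial has three arms, with outcomes measured at weeks 0, 8 and 16.

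**The concern.** A paired t-test is driven by the mean change divided by the SD of the change. The printed 1.81 appears to be the mean change divided by the baseline SD. The two agree only if the SD of the change happens to equal the baseline SD. With the figures as printed, the follow-up SD is twice the baseline SD, so that would require a correlation of exactly 1.

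The paired test also asks whether one arm changes from its own baseline. The analysis of primary interest asks whether change differs between arms, and a paired test has no control-arm change in it.

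What is at stake is the power statement, not the number enrolled. The text offers 7-8 per group at power above .95 as support, and a reader cannot tell from it what between-arm difference 10 or 12 retained patients per arm can detect.

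**Working it through.** All powers are exact noncentral-t values at two-sided alpha .05.

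**1. Reproducing the plan's figures.** Inputs from section 9: means 0.8 and 1.4, SEMs 0.1 and 0.2, n=11.

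- SD = SEM × √11: 0.1 × 3.317 = 0.332 before, 0.2 × 3.317 = 0.663 after.
- Change = 1.4 − 0.8 = 0.6.
- 0.6/0.332 = 1.809, which matches 1.81. The follow-up SD gives 0.90, the root-mean-square SD 1.14 and the average SD 1.21.
- Putting 1.81 into a paired t-test (noncentrality 1.81 × √n, n − 1 degrees of freedom) gives power 0.938 at n=6, 0.976 at n=7 and 0.991 at n=8. So 7-8 does follow once 1.81 is accepted. The question lies in the input.

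**2. The effect size that a paired test needs.** SD of change = √(s₀² + s₁² − 2·r·s₀·s₁) = √(0.11 + 0.44 − 2·r·0.22).

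- At r=.62 (an assumption, borrowed from the peripheral arterial disease calculation): √(0.55 − 0.2728) = 0.526, and 0.6/0.526 = 1.14.

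| r | effect size (change/SD of change) | power n=7 | power n=8 | power n=10 | power n=12 | n for power >.95 |
|---|---|---|---|---|---|---|
| 0 | 0.81 | 0.44 | 0.51 | 0.63 | 0.72 | 22 |
| .62 | 1.14 | 0.71 | 0.79 | 0.89 | 0.95 | 13 |
| .9 | 1.53 | 0.92 | 0.96 | 0.99 | 1.00 | 8 |

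Power of .95 requires an effect size of 1.650 at n=7 and 1.496 at n=8. On the printed figures these correspond to r of about .95 and .88. At n=12 and r=.62 the unrounded power is 0.948, so 13 are needed to exceed .95.

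**3. Sensitivity to rounding.** The inputs are printed to one decimal. A follow-up SEM of 0.15, which rounds to 0.2, gives at r=.62 an effect size of 1.534 and power 0.96 at n=8. Varying both SEMs and the mean change within rounding at r=.62 gives power from 0.33 to 0.97 at n=7 and from 0.38 to 0.99 at n=8.

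**4. The between-arm question on the same inputs.** Assume r=.62, zero change on placebo and an SD of change of 0.526 in both arms. The two-sample noncentrality is 1.14 × √(n/2). Power is 0.67 at 10 per arm and 0.76 at 12 per arm. If placebo instead keeps the baseline SD at both visits, its SD of change is √(2 × 0.11 × 0.38) = 0.289, and power (Welch, simulated) is about 0.83 and 0.90.

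**5. What the retained numbers can detect.** For a two-arm comparison of week 0 to week 16 change:

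| retained per arm | 80% power | 95% power |
|---|---|---|
| 12 | 1.20 SD of change | 1.54 SD |
| 10 | 1.32 SD | 1.71 SD |

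**6. Retained number.** 3 × 12 = 36 and 3 × 10 = 30. A total of 36 retained with 10 per group cannot hold in three arms.

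**7. The 8 (4 per group) figure.** Take noncentrality f²·N·m/(1 − r) with m=2 and r=.62, and enter the variance share directly as f². Then 84.5% gives power 0.965 at N=6 and 50% gives 0.966 at N=8, so both printed sizes are reproduced. On the plan's own residual-variance definition, the share is d²/(d² + 4), so 50% means a difference of 2 SD of change. Power is then 0.66 at 4 per group, but 0.988 at 10 and 0.997 at 12 per arm. The settings are inferred, because the plan does not print them.

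**The case against.** The denominator of 1.81 is not printed, and the match with the baseline SD is not the only one possible. A follow-up SEM of 0.15 with r=.75 gives an SD of change of √(0.11 + 0.2475 − 0.2475) = 0.332, and so also 1.81, as a proper paired effect size. The investigators may have had subject-level data. This stands: it limits the point to what the printed inputs establish.

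Nor did 7-8 set the sample size. The plan calls both source studies different from this trial, goes beyond their numbers because CD34+ cells may be scarce, and cites the team's own saxagliptin trial as confirming the calculation. At the planned numbers the named paired test does much better than at 7-8: 0.89 with 10 and 0.95 with 12, at r=.62. This also stands. A reader might infer that the trial is underpowered or needs more patients, but the documents do not support that. On the plan's two-group interaction inputs, power at 10-12 per arm exceeds .95.

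The plan does contain an interaction calculation and states its two-group limit. That is fair, but it covers two groups at two times, not three groups at three visits. The absence of power for the combination against dapagliflozin alone is a gap to disclose, not an error: the hypothesis says only that an additive effect may occur, and the primary objective names no such contrast.

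A reader might also take 8 (4 per group) as a demonstrated arithmetic slip. It is not, since a plausible software entry reproduces it.

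**Conclusion.** The statement that 7-8 subjects per group give power above .95 is not established by the inputs shown beside it. With the printed figures taken as exact, it needs a pre-post correlation of about .88 or .95. At a borrowed r=.62 the power is 0.79 (n=8) or 0.71 (n=7), and 13 subjects are needed. Because the correlation is not given and rounding alone could restore the claim, it is unsupported rather than false, and 13 is a central value and not a correction.

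Independently of that, a within-arm paired test does not size the group-by-time interaction. On the same inputs, with zero placebo change and equal SDs of change, between-arm power is about 0.67 (10 per arm) or 0.76 (12 per arm). The conflict between 10 and 12 retained per arm needs no assumption and must be resolved before any power statement can be read. The weight is moderate: the justification should be corrected, while enrolment of 45 is not called into question.

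**What to change.** Change the wording of section 9 and align the retained number elsewhere:

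1. Remove d=1.81 and the 7-8 per group figure as support for the sample size.
2. Reconcile 10 and 12 retained per arm across the Synopsis and sections 4, 8 and 9. A total of 36 corresponds to 12 per arm.
3. Add a statement such as: At two-sided alpha .05, unadjusted for multiplicity, a two-arm comparison of change from week 0 to week 16 has 80% power for 1.20 SD of change and 95% power for 1.54 SD with 12 retained per arm (1.32 and 1.71 SD with 10). This approximates the planned three-group, three-visit model. No power was calculated for the combination versus dapagliflozin alone.
4. Recheck the software settings behind 8 (4 per group), and state the effect-size entry and correlation used.

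This needs no extra patients or visits. The price is a conditional and less favourable power statement in place of the claim of more than .95, and one recheck of software settings.

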## **PRELIMINARY RESULTS**

Regarding Saxagliptin effect on CD34+ cells, serum biochemistry and arterial stiffness, our recently concluded results showed: Saxa significantly increased migration (using SDF1 $\alpha$  100ng/ml, p=0.04) with a trend of higher CFU count (p=0.07). There was an significant (p<0.001) increase in mean %CD34+ cells, Flow on MNCs showed more cells with double-

positive CD34 & CXCR4 ( $p=0.008$ ), and CD31 & CXCR4 ( $p=0.036$ ). [CXCR4 is a SDF1a receptor]. mRNA gene expression of CD34+ cells showed decreased inflammatory markers (Endothelin-1,  $p=<0.0001$ ), and a similar declining trend in apoptosis marker, p53 ( $p=0.026$ ). For AS (arterial stiffness), Pulse Wave Analysis (PWA) increased after visit 1 in the placebo arm unlike Saxa. Pulse Wave Augmentation Index @HR75 (A1x75), and radial Systolic BP declined (A1x75,  $p=0.037$  and SBP,  $p=0.06$ ) with Saxa vs placebo. Our conclusions from the study were: when Saxa was added to diabetes subjects with no known CVD, we noted improved number and migratory function of EPCs with increased SDF1a receptor, CXCR4, positivity. Gene expression analysis showed a reduced inflammatory and apoptotic state with improved AS. Our findings indicate how Saxa may help improve endothelial cell dysfunction, when added to Metformin, in early stages of diabetes, before macro-vascular complications appear.

Our results and literature indicates that the stem-cell “homing process” is based on the ability of DPP4 inhibitors to inhibit the degradation of SDF-1 and of its receptor CXCR-4, a pathway of importance for progenitor cell recruitment to ischemic tissue (myocardial or otherwise)

*As mentioned earlier*, we noted that CD34+ cells show mRNA expression of both SGLT1 and SGLT2 receptors with SGLT1 expression being higher than SGLT2. The expression of SGLT2 mRNA increased once the CD34+ cells were exposed to hyperglycemia (20mM glucose). Similarly, SGLT2 mRNA expression was higher in CD34+ cells from diabetic subjects versus non diabetic subjects. Increased expression of SGLT2 in presence of hyperglycemia would allow more glucose to enter the endothelial progenitor cells, which may lead to intra-cellular gluco-toxicity, which subsequently will lead to increased ROS formation, inflammation and cellular apoptosis.

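### Section 9 says the saxagliptin pilot verified the sample-size calculation for CD34+ function and gene expression, but that calculation covers cell number only and a significant pilot result cannot verify it

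*Combined protocol and SAP*

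**What the plan says.** Section 3 (Primary Objective) names three primary domains: CD34+ number, migratory function and gene expression.

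In Section 9 (Statistical Analysis) every power input is cell number. From a 4-week exercise study in arterial disease, "the interaction explained 84.5% of the variance in CD34+ cell concentration (a very large effect size" and "The correlation among repeated measures was $r=.62", so that power above .95 "would require a total sample size of 6 subjects (3 per group) each measured at 2 time points". From a pre-diabetes exercise study of 11 patients, cell number rose from 0.8 (SEM 0.1) "to 1.4 (SEM 0.2) after exercise, a pre-post effect size (Cohen's d) of 1.81"; for that effect, "using a 2-tailed paired t-test, with alpha=.05, for power $>.95$ , the number of subjects required would be 7-8, per group".

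The section then concedes that this rests mainly on number and turns to the saxagliptin pilot, which "takes into consideration CD34+ cell function and gene expression which verified our current statistical calculation", on the ground that its function and gene-expression measures reached significance. It adds that the pilot cohort was different, and that among published work "the closest will be our published study".

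Section 1 (Preliminary Results) reports p-values only. Migration and colony formation were "100ng/ml, p=0.04) with a trend of higher CFU count (p=0.07"), Endothelin-1 mRNA was p<.0001 and p53 mRNA p=.026. The pilot patients had no known CVD.

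**The concern.** A reader of Section 9 is told that a calculation with power above .95 has been checked for all three primary domains. For two of them nothing that could serve as a check is printed: no mean change, no SD, no sample size, no power. Significance in one study says that its observed effect was large relative to its standard error. It does not say that a repeat, or a different trial, would detect the effect with high probability.

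At stake is how the results are read. If migration or gene expression comes out null, the sentence invites the conclusion that a well-powered trial found no effect, when the plan never worked out its chance of finding one.

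**Working it through.** **1. The plan's own figure.** Two-sided paired t-test, alpha .05, d = 1.81 taken at face value: power is .938 with 6 patients, .976 with 7 and .991 with 8. The printed 7-8 per group reproduces. The mixed-model figure (84.5% of variance, r = .62, 6 patients in total) also reproduces: power is .985 or more under either common definition of the noncentrality. Both are calculations for cell number.

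**2. What the pilot p-values amount to.** Assume that each p-value is two-sided and from a single contrast (Section 1 does not say). If the true effect equals the observed one, a repeat at the same size has power of about Φ(z − 1.96), where z is the normal quantile at 1 − p/2. The n multiple for power .95 is (1.96 + 1.645)²/z² = 13.0/z².

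| Pilot result | p | z | Observed power | n multiple for .95 |
|---|---|---|---|---|
| Migration, SDF1 alpha 100 ng/ml | .04 | 2.054 | .54 | 3.1 |
| p53 mRNA | .026 | 2.226 | .60 | 2.6 |
| CFU | .07 | 1.812 | .44 | 4.0 |
| Endothelin-1 mRNA | <.0001 | >3.89 | at least .97 | below 1 |

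A t correction with 10 to 20 per arm moves migration only to .54-.55 and p53 to .62-.63. Observed power of .95 needs z = 3.605, that is p of about .0003.

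**3. How uncertain those figures are.** For migration the 95% interval for the true z is 2.054 ± 1.96 = 0.09 to 4.01. Two-sided power at those limits is .05 and .98. For p53 the interval is 0.27 to 4.19, giving .06 to .99. The 3.605 needed for .95 lies inside both intervals.

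**4. Which pilot results bear on this trial.** Appendix A keeps migration at SDF1 alpha 100 ng/ml, CFU, and p53 within the apoptosis genes. Endothelin-1 is not in its gene list. So the one pilot mRNA result with high observed power is for a gene this trial does not list, and the other is p53.

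**5. Carrying the pilot to this trial.** The pilot's size is not printed. Assume a two-sample contrast with k per arm. Then d = t(1 − p/2; 2k − 2) × √(2/k), entered into a two-sample t-test with n per arm. Example for migration with k = 12: t(.98; 22) = 2.183, d = 2.183 × .408 = .89, and power at n = 12 is .55. Both 10 and 12 are shown because Section 9 gives 36 retained and 10 per group in the same sentence.

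| Assumed pilot k per arm | Migration, n = 10 | Migration, n = 12 | p53, n = 10 | p53, n = 12 |
|---|---|---|---|---|
| 8 | .67 | .75 | .75 | .83 |
| 12 | .47 | .55 | .54 | .63 |
| 15 | .38 | .45 | .44 | .52 |
| 20 | .30 | .35 | .34 | .40 |

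Read the other way, 10 to 12 per arm reaches .95 for migration only if the pilot had about 4 to 5 per arm (k = 4 gives .97 and .99; k = 5 gives .91 and .95).

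**The case against.** Four points can fairly be made for the plan.

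First, a reader might infer that the plan claims power above .95 for migration and gene expression. It does not say so. That figure is attached only to cell number, and Section 9 admits that the calculation emphasises number. The wider claim is an implication of the word verified. This stands.

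Second, a reader might infer that the pilot contradicts high power. It does not. Observed power is a re-expression of the p-value, adds no evidence of its own, and spans .05 to .98 for migration. The pilot fails to establish .95; it does not rule it out. This stands too.

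Third, Endothelin-1 shows that not every pilot gene-expression result was marginal. That is true of the pilot, but the gene is not listed for this trial, so it cannot support power here. Likewise, CFU was openly reported as a trend, and Section 3 names migration as the function domain. The CFU result therefore qualifies the statement that the function measures were significant rather than overturning it.

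Fourth, the planned analysis is a group-by-time model over three visits, not a two-sample t-test, and may be more efficient. The pilot also differed in cohort, which the plan discloses. Both points limit the projections in step 5. They equally limit what the pilot can verify.

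None of this supplies the missing effect size, SD or power, so the sentence remains unsupported.

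**Conclusion.** The verification sentence is wrong as written. Power above .95 is derived for CD34+ number only, under effects seen with exercise, and nothing in the documents establishes power for migration or gene expression. For the kept endpoints the pilot p-values correspond to observed power of about .44 to .60 at the pilot's size, assuming two-sided single-contrast tests.

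It would go too far to conclude that a null migration result here would be a coin toss. That carries a pilot-size figure over to a trial with a different size, cohort and model. With an assumed two-sample pilot of 8 to 20 per arm, migration power is about .30 to .67 at 10 per arm and .35 to .75 at 12. The width of that range comes from information the sponsor holds and the plan does not print.

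A further limit on using the pilot is that no arm receives saxagliptin alone, so its separate effect appears here only as combination versus dapagliflozin.

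**What to change.** In Section 9:

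- Delete the clause saying that the pilot verified the calculation.
- State that power above .95 applies only to CD34+ number under an exercise-sized effect.
- Give the power, or the detectable difference, at 10 and at 12 evaluable patients per arm for migration at SDF1 alpha 100 ng/ml and for one gene listed in Appendix A, such as p53. Compute it from the pilot's mean difference in change and its SD, and print the pilot's n, test and contrast.
- Add the caveat that the pilot patients had no known CVD, and that the saxagliptin effect is seen here only in the combination versus dapagliflozin comparison.

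The cost is a few lines, from data the sponsor should already hold. N does not change. The drawback is that the stated power for these two domains will probably look less favourable.
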